Official title Cerebellar Transcranial Direct Current Stimulation in Parkinson's Disease

NCT number NCT04046055

Document date August 15, 2019

Prospective subjects will include 10 adults with mild-moderate PD that will be recruited to complete five randomly ordered cerebellar stimulation sessions (SHAM, unilateral 2 mA, unilateral 4 mA, bilateral 2 mA, and bilateral 4 mA), separated by at least 5 days. Each session will involve one visit to the Integrative Neurophysiology Laboratory (INPL) and will last for approximately one hour. We expect data collection to last 4-6 months. Cerebellar tDCS will be performed during all of the gait and balance tests. All five sessions will be the same, except for changes in tDCS stimulation. First, the Movement Disorder Society-Unified Parkinson's Disease Rating Scale Motor Section (MDSUPDRSIII) will be completed. Then tDCS will be donned and the stimulation period will begin. After 5 minutes of pre-activity stimulation, gait and balance testing will be performed in randomly-ordered blocks of randomized tests (i.e., block order randomized; each test randomized within the block; see below). The gait and balance blocks are expected to take approximately 20 minutes to complete, accounting for rest periods between the activities. Once all of the tests have been completed, and the stimulation period has ended (25 minutes), the tDCS device will be removed and the MDS-UPDRS III will be repeated to check for any acute changes in disease symptoms.

Gait block: 1) the fast 30-meter walk test (30mWT; walk 30 meters as fast as safely possible; walking characteristics and time taken to complete the task are the primary outcomes), 2) a 6-minute walk test (6MWT; walk continuously between two markers spaced 30 meters apart for 6 minutes at a brisk pace; total distance walked and walking characteristics are the primary outcomes), 3) two trials of the Timed Up and Go test (TUG; stand from a seated position, walk 5 meters, turn around, sit back down in the chair; time to complete the test is the primary outcome). Subjects will wear six motion sensors (OPAL inertial motion units) on the top of both shoes/feet, at both wrists, on the lower back (5th lumbar spine), and on the chest/sternum during the 30mWT and the 6MWT. The subjects will perform these walks in a cordoned-off hallway adjacent to the laboratory.

Balance block: 1) stand on a firm surface (directly on a force platform) for 1 minute with eyes open (balance characteristics [95% confidence interval of the total 2D area explored, center of pressure movement velocity in forward/backward and left/right directions] are the primary outcomes), 2) stand on a foam surface (6 cm foam pad placed on top of force platform) for 1 minute with eyes open (the same balance characteristics as above are the primary outcomes).

Subjects will be carefully watched and guarded against falling during all of the testing procedures. Study personnel will always be within arm's reach to help the subject recover their balance, when necessary.

Active cerebellar tDCS protocol: A tDCS device (Soterix) will deliver either 2 mA or 4 mA of direct current through two sponge surface electrodes (5cm x 7cm, soaked with 15 mM NaCl). Unilateral cerebellar tDCS will have the anode (positive electrode) placed 3 cm lateral to the inion, on the side ipsilateral to the most PD-affected side. The cathode (negative electrode) will be placed on the ipsilateral buccinator muscle (cheek). Bilateral cerebellar tDCS will have both electrodes placed 3 cm to either side of the inion, with the anode assigned to the most PD-affected side and the cathode assigned to the less PD-affected side. Total simulation time will be 25 minutes.

SHAM cerebellar tDCS session: Electrode placement for SHAM will be the same as the unilateral cerebellar montage in 50% of subjects (5 subjects) and the bilateral cerebellar montage in the other 50% of subjects (5 subjects). During SHAM, the tDCS device automatically performs a ramp-up and ramp-down (gradual increase/decrease in intensity) during the first 30

seconds and the last 30 seconds of the SHAM condition. During the intervening time (0:30 - 24:30), the stimulation is set to 0 mA.

The stimulation device will be placed in a backpack worn by the subjects during testing gait and balance testing. Both subjects and study personnel (except the PI) will be blinded to the stimulation condition; the PI will be the only one that knows the stimulation condition and will be the only one to operate the tDCS device. All other study personnel who help administer the gait and balance tests will be blind to the stimulation condition. The subjects will be asked to guess their stimulation condition at the end of each session. However, they will not be informed of the accuracy of their guesses until they have fully completed study participation (i.e., after the last session). We will also ask subjects to report any stimulation-related sensations (e.g., itching, burning, tingling, headache, etc.), and their magnitude (10- point Likert scale), they experienced during the session. These will be recorded on the demographic/data collection form (see attached).

There will be no long-term follow up.

STATISTICAL ANALYSIS

Performance on the gait and balance tests will be analyzed using a one-way repeated measures ANOVA with five conditions (SHAM, unilateral 2 mA, unilateral 4 mA, bilateral 2 mA, bilateral 4 mA) followed by Tukey adjusted pairwise comparisons.

The primary gait outcome measures will be time to complete the 30mWT, distance walked in the 6MWT, and the average time to complete the TUG test. Because we hypothesize that tDCS will improve the negative effects of gait, standard gait metrics during the two walk tests, including gait speed, cadence, stride length and time, step length and time, will be assessed with the OPAL motion sensor system.

The primary balance outcome measures will be 95% confidence interval ellipse (an ellipse that contains 95% of the 2D trace of the center of pressure [COP] movement during the balance tests) and COP velocity in the forward/backward and left/right directions.

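### Does splitting sham 5/5 between the two electrode montages, and analysing it as one level, spoil the comparisons with sham?

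*Combined protocol and SAP*

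**What the plan says.** The section on the SHAM cerebellar tDCS session splits the placement evenly. For one half it says: "Electrode placement for SHAM will be the same as the unilateral cerebellar montage in 50% of subjects (5 subjects"). The remaining subjects wear the second placement during sham, described there as "the bilateral cerebellar montage in the other 50% of subjects (5 subjects"). The two placements differ on the head. For the unilateral montage, the section on the active protocol says: "The cathode (negative electrode) will be placed on the ipsilateral buccinator muscle (cheek"). In the bilateral montage the electrodes sit on either side of the inion.

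The STATISTICAL ANALYSIS section plans a "one-way repeated measures ANOVA with five conditions", of which SHAM is one, "followed by Tukey adjusted pairwise comparisons". It has no term for the montage worn during sham and no contrast of all active sessions against sham. The documents do not say how a subject is allotted to a sham montage.

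**The concern.** Each active condition uses one fixed montage, while sham is a mixture of the two. In 5 of 10 subjects, then, an active-versus-sham difference compares sessions that differ in electrode position as well as in current. If the cheek pad, the skin sensation or the expectation attached to a placement changes walking or balance, part of that change would be read as an effect of stimulation, with opposite signs for the two montages. A pure placement effect could make one montage look better than sham and the other worse.

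Two remedies suggest themselves. One is a pooled contrast (mean of the four active sessions minus sham), which the 5/5 split balances for placement. The other is a model that treats unilateral sham and bilateral sham as separate cells.

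**Working it through.** **Inputs.** From the documents: 10 subjects, five conditions, sham split 5/5 (50% of 10 = 5, which agrees with the text). Assumed, because the documents give no figures: within-subject SD = 1, two-sided 5% level, and a placement effect d (unilateral minus bilateral, in SD units) from 0 to 1. Error df = (10-1)(5-1) = 36. Critical values: Tukey 2.871, unadjusted t 2.028.

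**Bias of the planned pairs.** Expected sham mean = (5·d + 5·0)/10 = d/2. Unilateral minus sham = d - d/2 = +d/2; bilateral minus sham = 0 - d/2 = -d/2. Had all sham sessions used one montage, two pairs would have bias 0 and two would have bias d in size. The summed squared bias over the four pairs is 4·(d/2)² = d² with the split and 2·d² without it. The split halves both this sum and the largest single bias.

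**Effect on error rates.** Chance of at least one false Tukey sham pair with no effect of current (200,000 simulated trials per row):

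| d (SD) | any false sham pair |
|---|---|
| 0 | 2.4% |
| 0.25 | 3.0% |
| 0.5 | 5.3% |
| 0.75 | 9.2% |
| 1 | 15% |

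Up to about half an SD the rate stays near the nominal 5%.

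**Remedy 1: separate the two shams (six cells, subject as block, 35 df).**
- Planned pair: variance 2/10 = 0.20, unadjusted half-width 2.028·√0.20 = 0.91.
- Active arm minus own-montage sham: (1 + 1/4)/5 + (1 - 1/4)/10 = 0.25 + 0.075 = 0.325, half-width 1.16.
- Mean squared error: 0.20 + d²/4 for the planned pair against 0.325. They are equal at d = √(0.125/0.25) = 0.71.
- Unilateral sham minus bilateral sham: 0.25 + 0.25 = 0.50, half-width 1.44.

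The remedy pays only if d exceeds 0.71 SD. The data can locate d only to within ±1.44 SD, about twice that threshold.

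**Remedy 2: the pooled contrast.** Variance (1/4 + 1)/10 = 0.125, half-width 2.028·√0.125 = 0.72, against 2.871·√0.20 = 1.28 for a Tukey pair. Placement bias is d/2 - d/2 = 0. The single-arm pairs, which are the quantities in question, are left as they were. Power for a 1 SD effect, contrast against at least one Tukey sham pair:

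| arms that work | contrast v pairs, unadjusted across outcomes | both Bonferroni over nine outcomes |
|---|---|---|
| four | 79% v 55% | 46% v 22% |
| three | 54% v 50% | 22% v 19% |
| two | 28% v 42% | 8% v 15% |
| one | 10% v 29% | 2% v 9% |

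Nine is the count in the analysis section: three gait outcomes ("time to complete the 30mWT, distance walked in the 6MWT, and the average time to complete the TUG test") plus three balance measures on two surfaces, since for the foam surface "the same balance characteristics as above are the primary outcomes". The contrast gains clearly when all four arms work, is close to level at three, and loses at two or one.

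**The case for a change.** The best case for change is that the stated hypothesis is general: "Because we hypothesize that tDCS will improve the negative effects of gait". The 5/5 split already balances the matching contrast for placement, yet no planned comparison uses it. Naming it would need a few sentences and no new sessions. If dropout upset the split, the one-way contrast would be biased slightly (1/2 - 5/9 = -0.056d with 5 and 4 completers), and equal montage weights in the six-cell model would remove that. Sham montage should also be allotted at random, since comparing the two shams is a between-subject comparison.

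The arithmetic is right, but the inference goes too far. The quoted clause concerns gait and introduces the motion-sensor metrics; it does not set a pooled hypothesis for the balance outcomes. The study has five distinct conditions and plans pairwise comparisons, so pooling all active sessions is a choice of another estimand. The contrast's interval is narrower partly because it escapes the Tukey adjustment: an unadjusted pair has half-width 0.91, not 1.28. The dropout bias belongs to a contrast that the plan does not use.

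What stands is small. The method of allotting sham montage is unstated, and sham-session guesses and sensation ratings could be tabulated by montage worn. Whether the montage is recorded cannot be judged, because the data collection form is referred to as attached but is not shown. These are points of reporting detail and change no conclusion.

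**Conclusion.** The concern does not hold. The observation that each sham pair is half montage-matched is correct, but it follows from a reasonable counterbalancing of one sham session over two montages, and no stated number or rule is shown to be wrong. Any bias is at most half the placement effect, and the documents give no evidence of its size. It would matter if d were large: at d = 1 SD the chance of a false sham pair reaches 15%. But the six-cell analysis costs precision (variance 0.325 against 0.20) and repays it only above 0.71 SD, which 5 sham sessions per montage cannot establish. The pooled contrast does not touch the pairs and trades power one way or the other according to how many arms work. Competent statisticians could choose either way, so the planned analysis can stand. These figures assume equal within-subject variances and correlations (sphericity), no dropout except where stated, and an assumed d between 0 and 1 SD.

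### Session order is described only as random and the ANOVA has no session term; balanced sequences plus a session term, adopted together, are a cheap safeguard for precision if performance drifts

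*Combined protocol and SAP*

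**What the plan says.** The opening design description has 10 adults "recruited to complete five randomly ordered cerebellar stimulation sessions", "separated by at least 5 days". Apart from the stimulation, the sessions are identical: "All five sessions will be the same, except for changes in tDCS stimulation". It does not say how the order is generated, and it mentions no Latin square, Williams set or other restriction.

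The document specifies order or balance in two other places. Within a session, the tests are randomised ("block order randomized; each test randomized within the block"), and the sham electrode montage is split 5/5 between subjects. Neither balances condition against session number.

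The Statistical Analysis section gives the model: "Performance on the gait and balance tests will be analyzed using a one-way repeated measures ANOVA with five conditions", with Tukey-adjusted pairwise comparisons. Condition is the only factor named beyond the repeated-measures structure. Practice, familiarisation and time effects are not discussed anywhere.

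**The concern.** Each subject performs the same timed walks, chair-rise test and force-plate tests five times. With four gaps of at least 5 days, this spans at least 20 days. Performance may change over that span for reasons unrelated to stimulation. Under simple random order, a condition can by chance fall mostly early or mostly late, and a model with condition alone cannot remove the resulting difference.

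What is at stake is precision. Ten subjects and ten Tukey comparisons per outcome leave little to spare: even with no drift, 80% power for one pair needs a true difference of 1.67 within-subject SD. The weakness lies in the combination of an order not stated to be balanced and a model without session, not in the ANOVA by itself.

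**Working it through.** **Inputs from the documents:** 10 subjects, 5 conditions, 5 sessions, a subject-plus-condition model, Tukey comparisons. The document gives no rationale for the sample size, so there is no power figure to reproduce.

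**Assumptions, not in the documents:** two-sided 5% level; a session effect that is additive and common to all subjects; the size of that effect; the true differences. All effects are in units of the within-subject SD. *s* is a linear change per session, so total drift from session 1 to session 5 is 4*s*.

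**Chance imbalance.** Under simple random order, sham is never given first with probability 0.8^10 = 10.7%. In simulation, at least one of the five conditions is never given first in 47% of trials.

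**Variance of a difference between two conditions.**

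- Current plan, simple random order: (2/10)(1 + Q), where Q is the sum of squared deviations of the five session effects from their mean, divided by 4.
- Linear drift: the deviations are -2s, -s, 0, s, 2s, so Q = 10s²/4 = 2.5s² and the variance is 0.2(1 + 2.5s²).
- One-off step g after session 1, then plateau: Q = 0.8g²/4 = 0.2g².
- Balanced order plus session term: 0.2, whatever the shape of the common session effect.

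**Degrees of freedom.** The current model has 4 × 9 = 36 error df and the model with session has 36 - 4 = 32. The Tukey critical values on the t scale are 2.871 and 2.889. The ratio 2.889/2.871 = 1.006 is the price of the term: intervals about 0.6% wider if nothing drifts.

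**Results for linear drift.** Effective subjects are 10/(1 + 2.5s²). Interval width is the current plan relative to the fix, 2.871√(1 + 2.5s²)/2.889. Power is for one Tukey pair, from the noncentral t.

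| s | Effective subjects, current plan | Interval width, current vs fix | Power at 1.2 SD | Power at 1.6 SD | Power at 2.0 SD |
|---|---|---|---|---|---|
| 0 | 10 | 0.6% narrower | 43.7% | 75.5% | 93.8% |
| 0.1 | 9.8 | 0.6% wider | 42.5% | 74.1% | 93.1% |
| 0.2 | 9.1 | 4% wider | 39.1% | 70.2% | 91.0% |
| 0.3 | 8.2 | 10% wider | 34.3% | 64.1% | 87.0% |
| 0.5 | 6.2 | 27% wider | 24.0% | 48.3% | 73.3% |
| Fix, any s | 10 | reference | 43.2% | 74.8% | 93.4% |

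The fix breaks even at s = 0.06-0.07, which is 0.24-0.28 SD of total drift. A gain of 5 power points needs s = 0.21-0.27 for differences of 1.0-2.0 SD, or about 0.8-1.1 SD of total drift.

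**Results for a step after session 1, then plateau.** Over differences of 1.0-2.5 SD the gain is 0.2-2.0 points for a step of 0.5 SD and 1.1-9.5 points for a step of 1.0 SD.

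**Validity.** In 40,000 simulated trials per cell, simple random order without the term gave family-wise error of 5.1, 5.0, 5.0, 4.9 and 5.1% at s = 0, 0.1, 0.2, 0.3 and 0.5. Nothing is inflated.

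**Each change on its own.**

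- *Balanced order without the term.* The estimates improve, but session variation stays in the residual and the test becomes conservative: family-wise error 5.0, 4.4, 3.2, 2.0 and 0.5% at the same values of s.
- *Session term under simple random order.* The design is not orthogonal. Over 40,000 random designs the mean variance is 0.226 rather than 0.2, and power at 1.6 SD is 68.2% against 75.5% for the current plan at s = 0. The term alone pays only from s = 0.23-0.26.
- *Both together.* Family-wise error stays at 4.7-5.1%, and simulated power at 1.6 SD and s = 0.3 is 74.8%.

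**The case against.** The planned analysis is a valid crossover analysis, so this is a choice between two valid designs. The documents do not show that performance changes across sessions, and a worthwhile gain needs sizeable drift: under 1 point at s = 0.1, and at most about 2 points for a 0.5 SD step after session 1. The larger trends, s = 0.3 and 0.5, mean 1.2 and 2.0 SD of total drift, for which the documents offer no evidence. A random order may also have been drawn from a balanced list in a document this short, particularly as the sham montage was deliberately split 5/5. Finally, the session term removes only drift common to all subjects.

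All of this stands as a limit on the size of the point, but it does not remove it. The cost of the fix is small and known, while the possible loss is open-ended. If the order is already balanced, omitting session makes the planned test conservative under drift, so the model still needs the term. Drift that differs between subjects stays in the error under either plan.

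**Conclusion.** The concern holds as a conditional loss of precision that is cheap to insure against. It is not bias and not inflated type I error. The actual loss is unknown: negligible if performance is stable or settles early, and several power points if total drift approaches 1 within-subject SD (at a true difference of 1.6 SD, 4.6 points at s = 0.2 and 10.7 at s = 0.3). These sizes rest on the assumed drift, differences and 5% level, on a session effect common to all subjects, and on complete data from 10 subjects. The change should be made because it costs so little, not because harm has been shown.

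**What to change.** State how the session order is generated, and make two changes together:

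1. Randomly assign the 10 subjects to a balanced set of sequences, either two randomised 5×5 Latin squares or a 10-sequence Williams design, so that each condition falls exactly twice in each session position.
2. Add session as a five-level categorical factor beside subject and condition, and keep the Tukey comparisons. With complete data an additive term in the planned ANOVA is enough; a mixed model with the same terms also uses subjects with missing sessions.

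If the order is already balanced, only the second change is needed. If it is simple random and can no longer be changed, keep the planned model.

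The cost is a fixed list of sequences and 4 of 36 error df, with no extra subjects or visits. With no session effect and 10 completers, the loss is at most about 0.65 power points, at true differences near 1.5 SD (at 1.6 SD, 75.5% to 74.8%). With 9 analysed it is up to about 1.5 points (69.0% to 67.5% at 1.6 SD). A session term does not remove carry-over between sessions; a Williams design only balances which condition directly precedes which.

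### No rule is given for missed or unusable sessions, and the planned ANOVA in its usual complete-case form would lose power that a mixed model on all available sessions partly keeps

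*Combined protocol and SAP*

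**What the plan says.** The opening paragraph of the study procedures plans for "10 adults with mild-moderate PD that will be recruited to complete five randomly ordered cerebellar stimulation sessions". The conditions and spacing are "SHAM, unilateral 2 mA, unilateral 4 mA, bilateral 2 mA, and bilateral 4 mA), separated by at least 5 days". That makes 10 × 5 = 50 sessions.

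The Statistical Analysis section says performance will be "analyzed using a one-way repeated measures ANOVA with five conditions", "followed by Tukey adjusted pairwise comparisons". It then lists the primary gait and balance measures.

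The documents do not say what happens to a subject with a missed session, a session stopped early or a failed recording. They mention no analysis set, replacement, imputation, software or data layout. They also give no alpha, effect size, standard deviation, power or expected dropout.

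**The concern.** A classical repeated measures ANOVA on one row per subject uses only subjects with all five values. One lost value then discards four valid ones for that outcome, and with 10 subjects each deletion removes a tenth of the trial. The same ANOVA fitted with subject and condition as factors can use incomplete subjects. The plan's wording allows both forms, and they give different answers once anything is missing. With no rule, the choice would be made after the data are seen.

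Loss is plausible. Each subject has five separate visits, stimulation sensations are expected enough to be scored, and outcomes depend on motion sensors and a force platform that could fail in a single session.

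**Working it through.** **Inputs from the documents.** 10 subjects, 5 conditions, one-way repeated measures ANOVA, Tukey adjustment over 5 × 4 / 2 = 10 pairs. There is no stated power figure to reproduce.

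**Assumptions.** Two-sided familywise alpha of 0.05. A pair difference of 1.67 within-subject SD (1.672 unrounded), chosen because it gives 80% power with full data. A proportion p of sessions lost independently at random: 3%, 5% or 10%.

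**Step 1. Complete subjects.** The expected number is 10 × (1 − p)^5, and the chance that all 50 sessions are usable is (1 − p)^50.

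| p | Expected complete subjects | Chance that all 50 are usable |
|---|---|---|
| 3% | 10 × 0.97^5 = 8.6 | 0.97^50 = 22% |
| 5% | 10 × 0.95^5 = 7.7 | 0.95^50 = 8% |
| 10% | 10 × 0.90^5 = 5.9 | 0.90^50 = 0.5% |

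**Step 2. Complete-case power for one pair.** With c complete subjects and within-subject SD of 1, the standard error is √(2/c), the error degrees of freedom are 4(c − 1), and the cut-off is the studentized-range value for 5 means divided by √2. Power comes from the noncentral t distribution.

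- c = 10: standard error √(2/10) = 0.447, 36 df, cut-off 2.87, noncentrality 1.672 / 0.447 = 3.74, power 80%.
- c = 9: standard error √(2/9) = 0.471, 32 df, cut-off 2.89, noncentrality 1.672 / 0.471 = 3.55, power 74%.

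Power is then averaged over the distribution of c.

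**Step 3. Power with all available sessions.** The variance of the pair difference comes from within-subject least squares (subject plus condition) on every observed session, with df = observations − subjects − 4. Power is averaged over simulated missing patterns.

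| p | Complete cases | All available | Share of lost power kept |
|---|---|---|---|
| 0 | 80% | 80% | not applicable |
| 3% | about 70% | about 78% | about three quarters |
| 5% | about 63% | about 76% | (76 − 63) / (80 − 63) = 76% |
| 10% | 46–47% | 71–72% | about three quarters |

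Repeat runs differ by about one point. A random-intercept model uses the same within-subject information plus some between-subject information.

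**Step 4. Other loss patterns (omnibus F, effect set to 80% power with full data).** If whole subjects leave after session 1 to 4, power with complete cases against all available sessions is:

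- one subject: 74% against 76–77%
- two subjects: 68% against 73%
- three subjects: 60% against 68%

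Only 36–43% of the lost power is kept. With exactly one missed session, the share kept runs from 11% to 92%, depending on which condition is lost and the shape of the effect.

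**Step 5. Type I error.** Simulation used 4,000 trials, nominal 5% and 5% of sessions missing (Monte Carlo standard error about 0.35 points).

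| Analysis | Equal variances | Unequal variances (epsilon 0.72) |
|---|---|---|
| Random intercept, Wald chi-square | 7.7% | 10.8% |
| Random intercept, F with residual df | 5.6% | 8.1% |
| Complete-case ANOVA, uncorrected | 5.4% | 7.6% |
| Complete-case ANOVA, Greenhouse-Geisser | 2.6% | 3.5% |

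Kenward-Roger was not simulated.

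**Step 6. Selective loss.** When poor 4 mA sessions were made more likely to be missing, the bias was −0.17 within-subject SD under both methods.

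**The case against.** **Is deletion the plan's rule?** A reader might infer that the plan drops a subject for any missed session. It does not say so. Deletion is the usual behaviour of the method run on one row per subject, and the all-available figures above come from the same ANOVA fitted as subject plus condition. What stands is narrower: no rule is stated, and the usual form of the named method loses data.

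**Will sessions be lost at all?** The documents give no rate. They set a minimum gap between sessions and no maximum, so a missed visit might be rescheduled. This stands. The rates are assumptions, and at zero loss the benefit is nil.

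**Does a mixed model always keep most of the lost power, at no cost?** A reader might infer this from the scattered-loss figures. It fails for withdrawals and can fail for a single missed session. There are also costs. A random intercept assumes equal variances and correlations across conditions, and large-sample Wald tests are too liberal with 10 subjects. The first is not a new weakness: the uncorrected ANOVA makes the same assumption and shows similar inflation (7.6% against 8.1%).

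**Would a session-number term undo the gain?** Partly. With full data and no true session effect, power falls from 80% to about 78% with a linear term and about 73% with a five-level term. At 3% loss, the five-level term gives 70.3%, against 70.1% for the complete-case ANOVA without it, so the gain disappears. This counts against bundling that term with the fix, not against the fix.

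**Does the model deal with loss due to poor tolerance?** No. The simulated bias was the same under both methods.

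**Conclusion.** The concern holds in this form: the plan has no rule for missed or unusable sessions, and the usual implementation of its named analysis would discard valid sessions in a 10-subject trial. Under scattered random loss of 3% to 10% of sessions, a pair powered at 80% falls to about 70% down to 46–47% with complete cases, against about 78% down to 71–72% with all available sessions.

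These figures rest on the assumed alpha, effect size, loss rates and independence of losses, none of which the documents supply. The documents do not support saying that the plan prescribes deletion, that loss is certain, or that the alternative is free or removes bias. The change is still worth making. It settles the analysis in advance, and with complete data and no session term it reproduces the planned ANOVA whenever the estimated between-subject variance is positive.

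**What to change.** In the Statistical Analysis section, replace the ANOVA sentence with a prespecified linear mixed model for each outcome:

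- Use all available sessions, with a fixed effect for condition and a random intercept for subject, fitted by REML with Kenward-Roger degrees of freedom. Do not use large-sample Wald tests.
- Take the Tukey-adjusted pairwise contrasts from this model.
- Define an unusable session for each outcome.
- State that the model assumes data are missing at random, and equal variances and correlations across conditions.
- Report the number of missing sessions and the reasons, by condition, and give a complete-case repeated measures ANOVA as a sensitivity analysis.

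Whether to add session number is a separate decision. It is not needed here and has the power cost given above. If it is added, say whether it is linear or five-level.

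The cost is a few sentences in the plan and one extra analysis, with no added subjects or visits.

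### Should the Tukey comparisons of the five stimulation conditions be replaced by a step-down all-pairs test?

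*Combined protocol and SAP*

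**What the plan says.** The Statistical Analysis section states: "Performance on the gait and balance tests will be analyzed using a one-way repeated measures ANOVA with five conditions", "followed by Tukey adjusted pairwise comparisons". The five conditions are sham and two electrode montages at two intensities each. No pair is singled out, so the family is all pairs. No step-down or closed form is named, so the ordinary single-step Tukey test is the natural reading.

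The opening description gives the sample: "Prospective subjects will include 10 adults with mild-moderate PD", each attending all five sessions. The same analysis covers the gait and balance outcomes. On the foam surface, "the same balance characteristics as above are the primary outcomes".

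The plan states no significance level, effect size, SD or power target. It has no sphericity check or correction, and it does not mention simultaneous confidence intervals.

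**The concern.** Single-step Tukey holds every pair to the cutoff needed when all five conditions are equal. Once one condition truly differs, at most 6 of the 10 pairs can still be equal (the pairs among the other four), so the cutoff is stricter than 5% control requires. A closed test uses that slack: it declares a pair different only if every grouping of the conditions that treats the two as equal is rejected, each at its own smaller or equal cutoff. In theory it finds everything Tukey finds, and sometimes more, at the same nominal error.

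With 10 subjects, power per pair is scarce. The question at stake is which of the four active settings differ from sham and from one another, and the remedy would cost no extra visits. A method that is never worse on rejections and sometimes better looks like a free gain left on the table.

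**Working it through.** **Inputs.** From the documents: 10 subjects, 5 conditions, all-pairs Tukey. Derived: 5×4/2 = 10 pairs; error df (10−1)(5−1) = 36; pair standard error √(2/10) = 0.447 error SD. Assumed, because the plan is silent: two-sided 0.05 per outcome, 10 completers, and effects in units of the within-subject error SD. The plan has no figure of its own to reproduce.

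**Cutoffs on |t|, 36 df.** For one group of k equal conditions the cutoff is the 95% point of the studentized range divided by √2. For k = 5 this is 4.060/√2 = 2.871, which is Tukey's cutoff for every pair. The closed test covers all 51 groupings with at least one equal pair:

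| Sizes of equal groups | 5 | 4 | 3+2 | 3 | 2+2 | 2 |
|---|---|---|---|---|---|---|
| Cutoff | 2.871 | 2.693 | 2.579 | 2.444 | 2.331 | 2.028 |

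The 3+2 and 2+2 values come from numerical integration over the error SD. None exceeds 2.871, so a pair that passes Tukey passes every grouping that contains it. No Tukey rejection was lost in simulation.

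**Any false rejection under sphericity.**

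| Pattern | Tukey | Step-down |
|---|---|---|
| All five equal | 5.0% | 5.0% |
| One large effect | 3.3% | 5.0% |
| 3+2 split | 2.5% | 5.0% |
| 2+2+1 split | 1.3% | 5.0% |

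**Power per truly different pair under sphericity.** For Tukey this is the chance that a noncentral t on 36 df, with noncentrality (effect)/0.447, exceeds 2.871 in absolute value. At 1.0 SD the noncentrality is 2.24 and power is 28%.

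| Pattern | Effect (SD) | Tukey | Step-down |
|---|---|---|---|
| All four active settings differ from sham | 0.5 | 5% | 6% |
| Same | 1.0 | 28% | 33% |
| Same | 1.5 | 68% | 75% |
| Only the two 4 mA settings differ | 1.0 | 28% | 35% |
| Same | 1.5 | 68% | 78% |

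Tukey with 11 to 12 subjects would match the all-four gains: at 1.0 SD its power is 31.9% with 11 and 35.9% with 12, around the step-down's 33.1% with 10. When all four settings work equally at 1.0 SD, the chance of at least one sham finding is 55% by either method. In that pattern the two methods agree on all 10 pairs in about 81% of simulated trials, and at 0.5 SD in about 96%.

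**Any false rejection without sphericity.** The covariance structures are assumptions. Figures are simulated and carry an error of about 0.2 point.

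| Structure | True pattern | Tukey | Step-down |
|---|---|---|---|
| Sham variance ×2 / ×3 | One large active effect | 4.2% / 5.2% | 6.1% / 7.3% |
| 4 mA variances ×2 / ×3 | Sham far from four equal settings | 4.7% / 5.9% | 6.7% / 8.1% |
| 4 mA variances ×2 / ×3 | 2+2+1 (2 mA pair, 4 mA pair, sham) | 2.4% / 3.5% | 6.8% / 8.5% |
| Correlation 0.8 within montage, 0.2 elsewhere | 2+2+1, as above | 2.4% | 6.9% |

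Under the global null the two methods err identically (5.5% or 6.5% with sham variance doubled or tripled). The methods part in the partial patterns, where Tukey's slack absorbs much of the inflation and the step-down test has already spent it.

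**Intervals.** Tukey's interval half-width is 2.871×0.447 = 1.28 error SD. A pair can be rejected by the step-down test alone when its observed difference lies between 2.028×0.447 = 0.91 and 1.28 error SD. Its Tukey interval then includes zero.

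**The case for a change.** The best case for changing runs as follows. The inclusion result is analytic and needs no effect size. The sponsor's all-pairs family is kept. The gain is largest on the most useful question, identifying every working setting against sham: at 1.5 SD this rises from 41% to 53% when all four work and from 54% to 69% when two do. When only the two 4 mA settings work at 1.0 SD, even the chance of at least one true sham finding rises, from 41% to 47%. Both methods assume sphericity, so its failure could be said to count against both. The plan promises no intervals, so nothing promised would be lost.

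The inclusion result and the power gain under sphericity stand. The claim that 5% error is kept stands only under sphericity. With different montages and intensities, equal variances and correlations cannot be taken for granted, and the two methods do not suffer equally when they fail. The larger gains sit at 1.5 SD, where Tukey already has 68% power per pair; at 0.5 SD the gain is one point. The error argument also covers only false rejection of equal pairs, not a claim in the wrong direction. Finally, the change is more than a wording edit: it needs numerically derived cutoffs and a rule for subjects who miss some sessions, because pair standard errors then differ.

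Multiplicity across outcomes does not bear on the choice, since neither method addresses it.

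**Conclusion.** The observation is correct, but it describes an optional efficiency choice and not a fault in the plan. Tukey is a recognised all-pairs procedure, valid under the assumptions the plan already makes. The alternative buys about 1 percentage point of power per true pair at 0.5 SD, 5 to 7 at 1.0 and 7 to 10 at 1.5, which for the all-four pattern is worth one to two extra subjects. In exchange it gives up decisions that match the Tukey intervals, and it gives up the margin that kept Tukey at about 2.4% to 6% where step-down error was about 6% to 8.5%.

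The power figures rest on an assumed 0.05 level per outcome, 10 completers, sphericity and assumed effect sizes; the error figures without sphericity rest on assumed covariance structures. The cutoffs need only the 0.05 level and 36 error df. Reasonable statisticians could choose either method, so the plan can stay as written on this point.
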